5.7.2 Handling of Participant Withdrawals or Termination

Subjects that withdraw from the study will continue to receive usual care from their cardiologist. Every effort will be made to capture the reason for subject withdrawal and to ascertain if any adverse events or serious adverse events occurred, which would be immediately reported to the IRB and study sponsor. Subjects who fail to comply with baseline data collection activities after signing the consent, despite several efforts to contact the subject with no response from the subject, will be replaced.

5.8 Premature Termination or Suspension of Study

This study may be temporarily suspended or prematurely terminated if there is sufficient reasonable cause. Written notification, documenting the reason for study suspension or termination, will be provided by the suspending or terminating party to the IRB and funding agency. If the study is prematurely terminated or suspended, the PI will promptly inform the IRB and will provide the reason(s) for the termination or suspension.

Circumstances that may warrant termination or suspension include, but are not limited to:

- Determination of unexpected, significant, or unacceptable risk to participants
- Demonstration of efficacy that would warrant stopping
- Insufficient compliance to protocol requirements
- Data that are not sufficiently complete and/or evaluable
- Determination of futility

Study may resume once concerns about safety, protocol compliance, data quality are addressed and satisfy the sponsor, IRB and/or FDA.

5.9 Study Behavioral or Social Intervention(s)

This study is testing a behavioral intervention that includes assessment (using PAVS), promotion (by the cardiologists) and monitoring of PA (by Fitbit) for patients seen in Preventive Cardiology Center.

5.9.1 Administration of Intervention

This intervention will be incorporated into clinical care in the Preventive Cardiology Center. The patient will answer the 3-question PAVS: 1) "On average, how many days per week do you

CONFIDENTIAL

This material is the property of the NYU School of Medicine and Langone Medical Center. Do not disclose or use except as authorized in writing by the study sponsor
Interventional Template Version: 11 January 2019

engage in PA or exercise?"; 2) "On average, how many total minutes of PA or exercise do you perform on those days?"; and 3) "Describe the intensity of your PA or exercise (light=casual walk, moderate=brisk walk, or vigorous=jogging)" in the EHR when they check in for their appointment. During their clinical visit with their cardiologist, if they achieve < 50% of recommended PA on average, the cardiologist will make a referral to cardiac rehabilitation (if appropriate) or make a PA recommendation to increase intensity or duration of PA. The patient can choose to participate in the remote monitoring using the Fitbit activity monitor. The Fitbit data will sync to their MyChart account in the EHR.

5.9.2 Procedures for Training Interventionalists and Monitoring Intervention Fidelity

The PI will conduct intervention fidelity checks on a monthly basis. The PI will be given a monthly report generated from the Epic analyst team which will include data on completion of the PAVS questions and the cardiologists' referral system for PA. If use of the PAVS or referral system is < 80% for the month, the PI will meet with the medical assistant or cardiologist to discuss strategies to improve use. If the patient subject does not wear the Fitbit for at least 5 days per week, they will be contacted by the PI or RA to discuss strategies to improve adherence.

5.9.3 Assessment of Subject Compliance with Study Intervention

If the patient subject has less than 5 days of valid Fitbit wear (less than 10 hours/day) for the week, the PI or RA will call the patient subject and discuss strategies to improve adherence. We will utilize the resources of the NYU Recruitment and Retention Unit as needed. We will follow up with the patient subjects with the method they prefer (phone, email, text) for Fitbit data collection and to schedule the follow-up data collection at 3 months.

6 Study Procedures and Schedule

Baseline visit: After their visit with their cardiologist, interested patient subjects will have the study described and consent and enrollment in the study if desired. Baseline data collection will take place. For the next 3 months the patient subject is asked to wear the Fitbit and sync to their app on their phone. At 3 months patient subjects will return to the clinic for follow-up assessment.

A sample of 10 patient subjects will be asked to provide feedback about the study at this follow-up visit. A semi structured interview guide will be used to obtain feedback about the intervention from their perspective. Upon study completion, qualitative interviews using a semi-structured interview guide with the three cardiologists and the one nurse practitioner in the Center who works with one of the cardiologists will explore the acceptability, clinical utility and usability of the implementation.

6.1 Study Procedures/Evaluations

6.1.1 Study Specific Procedures

Phase 1. The PI will train the medical assistants on the collection of the PAVS (in case the patient had not entered the kiosk data). The PI will meet the CTSI Patient Advisory Council for feedback on how to appeal to participants and improve engagement. The PI will review the plan and the American College of Sports Medicine exercise screening guidelines with the cardiologists and elicit final questions or feedback.²⁹

CONFIDENTIAL

This material is the property of the NYU School of Medicine and Langone Medical Center. Do not disclose or use except as authorized in writing by the study sponsor
Interventional Template Version: 11 January 2019

Phase 2. Each patient in the Center is seen by the medical assistant for the assessment of their vital signs and confirmation of the PAVS completion in the check-in kiosk. During the patient's visit with the cardiologist, an EHR decision support tool will be presented as an alert to the cardiologist for patients who are not achieving at least **50%** of recommended PA levels. This threshold was chosen for two reasons. A higher threshold (e.g. < 90%) would create many more alerts for the cardiologist and possibly lead to 'alert fatigue'. Second, our focus will be on the least active patients. The cardiologist will choose and acknowledge the PA promotion recommendations they discussed with the patient: #1) patients with a diagnosis appropriate for cardiac rehabilitation³⁰ will be given a suggested verbal referral to cardiac rehabilitation services; and/or #2) patients who are not eligible for a cardiac rehabilitation referral (or do not want to attend) will be given a verbal recommendation to start engaging in PA, or increase intensity and/or duration of PA with an agreed upon goal for the next 3 months. Patients who should not increase PA due to certain medical diagnoses (e.g. aortic stenosis, unstable angina) will be excluded. The cardiologist will inform these patients about the remote PA monitoring. Upon contact, the PI will describe the study, and if patients agree to participate, obtain consent, enroll the participant and collect baseline data. The PI will give participant a Fitbit Zip, set up an account with a study ID and ask them to wear the Fitbit Zip during all waking hours. NYU Langone has implemented integration of Fitbit Zip data into the EHR which requires the patient to sync their Fitbit account to the patient portal (MyChart) once and step counts will then sync to EHR and can populate the cardiologists' note. Participants will be given the first compensation for their time (\$50 gift card) at completion of this baseline visit. One week after enrollment, a follow-up call will be made to the participants to answer questions. The PI will review the PA data weekly to ensure that participants are correctly wearing the Fitbit Zip and data are being downloaded and synced. The PI will make follow-up reminders as needed. Data will be downloaded from each participant's record at the end of three months. At three months, the PI will meet with the participant to collect follow-up data and provide the second incentive of \$50. Qualitative interviews to assess the acceptability of the intervention (including previous use of smart devices) will be collected in a purposive sample (n=10) of participants with varying levels of PA and varying degrees of adherence to the Fitbit Zip. The participant may keep the Fitbit. In the event virtual recruitment and data collection is needed due to Covid-19 restrictions, or to minimize the amount of in-person time involved for the consent, the PI will discuss the study by telephone with the interested patient. If they meet inclusion criteria they will be sent via email an electronic link to the consent on REDCap (REDCap consent link attached). The PI will discuss the study and review the consent with the interested patient by telephone page by page. If the patient is interested in participation, they can electronically sign their consent.

Measures:

Baseline visit after consent and enrollment in the study. Data collection will include:

Physical Activity Vital Sign (PAVS): 3 questions as described above when patients check in for their clinical appointment.

Stages of Change will be assessed with a Readiness to Change Ruler.³¹ A straight line is drawn on paper representing the process of change (from 1= 'not ready to change' to 10='already changing').

Cardiorespiratory fitness (CRF) will be measured by the six-minute walk test, a valid and reliable measure for use in field testing of CRF.³² The 6MWT will be conducted in a quiet hallway using a 30-meter track with standard instructions.³³

BMI will be calculated by height and weight measured at the time of the Center visit on a balance beam scale.

Waist Circumference will be measured to the nearest inch using standard technique.³⁴ Blood pressure (BP) will be measured in right arm (unless contraindicated) after sitting for 5 minutes and repeated after a 5-minute interval. Both will be recorded and the average used in analyses.

CONFIDENTIAL

This material is the property of the NYU School of Medicine and Langone Medical Center. Do not disclose or use except as authorized in writing by the study sponsor
Interventional Template Version: 11 January 2019

Total cholesterol, HDL, and triglycerides will be measured by CLIA-waived Alere Cholestech LDX® Analyzer which is certified by the Center for Disease Control's Lipid Standardization Program and Cholesterol Reference Method Laboratory Method Network. This will be measured by a single fingerstick using standard aseptic technique.

The Framingham Heart Study Risk Score (10-year risk) will be calculated using the appropriate risk model based on participants' age, gender, diabetes status and prior coronary heart disease.³⁵ Two covariates that have an inverse association with PA, depressive symptoms and general health-related quality of life,^{36,37} will be assessed.

Depressive symptoms will be measured by the PROMIS Depression Short Form 6a, a reliable ($\alpha = .92$) 6-item survey with strong convergent validity ($\alpha = .72-.84$) which assesses negative views of self, social cognition, decreased positive affect and engagement³⁸ and is also available in Spanish.³⁹ It will be scored with REDCap auto-score.

General health-related quality of life will be measured by the common data element 36-Item Short Form Health Survey (SF-36) v-1, a reliable measure ($\alpha = .90$) of physical and mental health with strong criterion validity, which is also available in Spanish.⁷⁷⁻⁸⁰ PROMIS surveys will be scored using the REDCap auto score for accuracy.

Clinical data will be collected from the EHR including potential confounding variables: age, sex, race/ethnicity, primary diagnosis, smoking status, and comorbidities (summarized as continuous data by the Charlson Comorbidity Index).⁴⁰

Sociodemographics, collected using common data elements survey⁴¹ and clinical data from the EHR will be collected at baseline. Fitbit steps will be collected daily for 3 months.

All other data will be collected baseline and at 3 months.

In the event all data collection must be remote or the subject prefers remote data collection, the PI will use baseline data from the electronic health record. The six-minute walk test can be administered remotely via an app on the subject's mobile phone with the distance walked emailed to the PI. BMI and blood pressure taken on the day of their recent clinical visit will be used for baseline data. A measuring tape will be mailed to the participant with instructions on measurement of waist circumference using standard technique. The PI or RA can schedule a videoconference to review the technique of measuring waist circumference. The most recent total cholesterol, HDL, and triglycerides results from the EHR will be used. All other baseline data collection will remain as planned.

If at 3-months remote data collection continues for a subject, the six-minute walk test will be done remotely with the mobile app. BMI and blood pressure will be used from the most recent office visit, as close to the 3-month follow-up date as possible. The patient will measure waist circumference as directed using standard technique and reviewed via video conference. The next available lab data for total cholesterol, HDL and triglycerides will be used. All other 3-month data collection will remain as planned.

If at 3-months in-person data collection is possible, the PI will resume in-person data collection as planned and meet the subject at the preventive cardiology center for data collection.

The PRISM²⁶ will be used to collect process evaluation data throughout the implementation. This will include data on the reach (proportion that participate in intervention), efficacy (success rate if implemented as designed), adoption (proportion that adopt intervention), implementation (extent to which intervention is implemented as intended) and maintenance (extent to which program is sustained over time) of the PA promotion intervention

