4.2 Study Endpoints

4.2.1 Primary Study Endpoints

For this feasibility study, we will implement the intervention (PA assessment using the PAVS; counseling by the cardiologists; and PA monitoring of patients wearing a Fitbit) for 12 months. Patient subjects who enroll in the PA monitoring will wear the Fitbit for 3 months. Primary endpoints include: patients' cardiovascular risk profile (PA, cardiorespiratory fitness, BMI, waist circumference, blood pressure, lipids and Framingham Heart Study Risk Score).

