9.1 Statistical and Analytical Plans (SAP)

Aim 1. Analysis will be performed using SAS 9.4. Surveys will be administered using the Research Electronic Data Capture (REDCap) system,⁴² a secure web-based tool licensed and supported by NYU. Standard descriptive statistics will be used to describe baseline sociodemographic and clinical characteristics. Mean scores and standard deviations as well as Cronbach's α will be calculated on questionnaires to confirm reliability of study instruments in our sample. Week 2 of the Fitbit Zip PA data will be used as baseline to assure the participant is accustomed to the device and to minimize the effect of reactivity, which can last approximately one week.⁴³ To calculate total minutes/week of PA from PAVS, the following standard calculation will be used:⁴⁴ light activity will be multiplied by 0 (light activity is not included in PA recommendations but is collected to acknowledge all attempts at PA and encourage increased intensity); moderate activity is multiplied by 1; vigorous activity is multiplied by 2 (one minute of vigorous activity being equal to two minutes of moderate activity). Paired t-tests will be used to assess changes in average PA from week 2 to three-month follow-up using PAVS and Fitbit Zip data. Using Fitabase software which allows for high resolution data, we will compare minutes of PA in three levels of intensity (light, moderate, and vigorous) as well as minutes spent in sedentary behavior. We will report the percentage of weeks each participant achieves the recommended levels of PA during the monitoring period and will assess weekly PA trends. We will compare improvements in PA by levels of protocol adoption by the HCP (e.g. 100% vs. 50% adoption). At 3 months we will compare mean minutes of moderate-to-vigorous PA between those who report achieving recommended levels of PA by the PAVS to those who do not. Paired t-tests will be used to assess changes in readiness to change number, the 6MWT, BMI, waist circumference, systolic and diastolic BP, lipids, and Framingham Heart Study Risk Score. To assess meaningful improvement in CRF, we will report the percent of participants who achieve a clinically important difference of 25 meters in the 6MWT.⁴⁵ Bivariate analyses will compare all CVD risk factors, as well as other potential confounders (e.g. age, sex, race/ethnicity, depressive symptoms, quality of life, comorbidities), between those who achieve PA recommendations and those who do not.

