9.3 Sample Size

The purpose of this pilot study is to test our study protocol and obtain preliminary clinical efficacy data on patient outcomes. With a type 1 error of 5% and 80% power, a sample of 59 participants will allow us to detect a minimal clinically important difference (seen in adults with CVD) in the six-minute walk test of 25 meters.⁴⁵ (effect size =0.33) There is a potential for 20% attrition based on the PIs previous work. With a type 1 error of 5% and 80% power, this sample of 47 participants will allow us to detect an effect size of 0.41 (28 meters for the six-minute walk test, an increase of 9,710 in weekly step count, and an increase of 10% of the sample achieving recommended levels of PA) and will have 80% power to detect a small effect (R^2 of .09 to .11) associated with a predictor assuming up to 4 covariates which have a combined R^2 of .4 to .2

CONFIDENTIAL

This material is the property of the NYU School of Medicine and Langone Medical Center. Do not disclose or use except as authorized in writing by the study sponsor
Interventional Template Version: 11 January 2019

with change in average weekly PA. Given our timeline and weekly volume of patients we believe it is feasible to enroll a sample of 59 participants.

10 Source Documents and Access to Source Data/Documents

Access to study records will be limited to IRB-approved members of the study team. The investigator will permit study-related monitoring, audits, and inspections by the IRB, the sponsor, and University compliance and quality assurance groups of all study related documents (e.g. source documents, regulatory documents, data collection instruments, study data etc.). The investigator will ensure the capability for inspections of applicable study-related facilities (e.g. pharmacy, diagnostic laboratory, etc.).

Participation as an investigator in this study implies acceptance of potential inspection by government regulatory authorities and applicable University compliance and quality assurance offices.

11 Quality Assurance and Quality Control

QC procedures will be implemented beginning with the data entry system and data QC checks that will be run on the database will be generated.

Following written SOPs, the PI will verify that the clinical trial is conducted and data are generated, documented (recorded), and reported in compliance with the protocol and GCP.

12 Ethics/Protection of Human Subjects

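### Waist circumference, a listed primary endpoint, is recorded in person only to the nearest inch, which adds avoidable random error to its change scores

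*Combined protocol and SAP*

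**What the plan says.** Section 6.1.1 (Measures) sets the recording unit: "Waist Circumference will be measured to the nearest inch using standard technique". No other section gives a finer one, and no reason for the unit is stated.

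Section 4.2.1 lists the primary endpoints as the cardiovascular risk profile: "PA, cardiorespiratory fitness, BMI, waist circumference, blood pressure, lipids and Framingham Heart Study Risk Score". For timing, Section 6.1.1 says of everything except the baseline-only items and the daily steps: "All other data will be collected baseline and at 3 months". Section 9.1 gives the test: "Paired t-tests will be used to assess changes in readiness to change number, the 6MWT, BMI, waist circumference, systolic and diastolic BP, lipids". The quantity analysed is therefore the difference between two readings.

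For remote collection, Section 6.1.1 says: "A measuring tape will be mailed to the participant with instructions on measurement of waist circumference using standard technique". It does not repeat the recording unit there. No repeat reading is stated for waist. For blood pressure, by contrast, two readings are taken: "Both will be recorded and the average used in analyses".

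**The concern.** One inch is coarse beside the change that the trial could detect. With 47 completers and an SD of 3 cm, the detectable mean change is about 1.25 cm, roughly half the recording unit. A participant whose waist changes by that amount will be recorded as unchanged about half the time and as changed by a full inch the rest of the time. No second reading is stated that would average out part of the rounding.

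At stake is the precision of one primary endpoint in a small pilot that is meant to supply preliminary effect sizes. Detail lost when the reading is written down cannot be recovered in the analysis.

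**Working it through.** **Inputs from the documents.** The unit is 1 inch = 2.54 cm (Section 6.1.1). There are two readings per participant (Section 6.1.1), a paired t-test (Section 9.1), and 47 evaluable participants out of 59 (Sections 5.6 and 9.3). Type 1 error is 5% and power 80% (Section 9.3).

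**Input that must be assumed.** No SD, target difference or power is given for waist change. The SD that matters is the total SD of the unrounded change, including tape placement and observer error. I use 2 to 8 cm and treat 3 to 8 cm as the main range. The test is taken as two-sided, because Section 9.3 does not say.

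**The plan's own figure.** Section 9.3 gives a detectable effect size of 0.41 for 47 participants. The normal approximation gives n = ((1.960 + 0.842)/0.41)² = 46.7, so 47. The exact noncentral t gives 78.6% power at 0.41 and a detectable effect of 0.417 at 80%. The stated figure is reproduced to within rounding, and 0.417 is used below.

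**Rounding error.** A reading rounded to unit u carries near-uniform error with variance u²/12, and a difference of two such readings carries u²/6.

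- One reading: 2.54²/12 = 0.538 cm², SD 0.73 cm.
- One change score: 2.54²/6 = 1.075 cm², SD 1.04 cm.
- Largest possible error in one change score: half an inch at each visit, so 1 inch (2.54 cm).

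**Effect on the test.** The variance ratio is 1 + 1.075/SD². The equivalent number of completers is 47 divided by that ratio. The detectable change is 0.417 × SD without rounding and 0.417 × √(SD² + 1.075) with it. Power is for a true effect of 0.417 SD, which gives 79.9% without rounding.

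| Assumed SD (cm) | Rise in variance | 47 completers worth | Detectable change (cm) | Power with rounding |
|---|---|---|---|---|
| 2 | 26.9% | 37.0 | 0.83 → 0.94 | 70.0% |
| 3 | 12.0% | 42.0 | 1.25 → 1.32 | 75.3% |
| 4 | 6.7% | 44.0 | 1.67 → 1.72 | 77.3% |
| 5 | 4.3% | 45.1 | 2.08 → 2.13 | 78.2% |
| 6 | 3.0% | 45.6 | 2.50 → 2.54 | 78.7% |
| 8 | 1.7% | 46.2 | 3.34 → 3.36 | 79.3% |

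**Check by simulation.** One million pairs were drawn for each SD, with an assumed baseline mean of 105 cm and SD of 14 cm. At a change SD of 3 cm, the observed SD was 3.177 cm against 3.174 cm from the formula. The mean change was −1.246 cm rounded and −1.247 cm unrounded, so rounding did not bias it. The share of changes recorded as exactly zero was 29.5% at 3 cm and 22.6% at 4 cm.

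**What finer units leave.** The SD added to a change score is 0.52 cm at a half inch, 0.26 cm at a quarter inch, 0.13 cm at an eighth (1.037/8) and 0.04 cm at 0.1 cm. Added variance scales with u², so a half inch removes 75% of it and a quarter inch about 94%.

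**The case against.** The best case against acting is that little depends on this. The trial is a one-group pilot, and waist is one of seven components of the risk profile. The sample size in Section 9.3 is argued from the six-minute walk test, step counts, attainment of activity levels and a regression, not from waist. No responder threshold for waist is planned, so zero or full-inch jumps in single scores matter only through the group mean. Self-measurement, or a change of mode between visits, would tend to raise the total SD and so shrink the relative loss. All of this stands and keeps the point minor. It gives no reason to prefer the coarser unit.

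Four stronger readings are tempting, and the documents do not support them.

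- A reader might infer that every change score carries this error. The inch rule is stated once, and the remote text restates no unit. If only one of a pair is rounded to the inch, the added variance is 0.538 rather than 1.075 cm².
- A reader might infer that rounding hides real change and pulls the estimate towards zero. It adds noise to single scores but leaves the mean essentially unbiased.
- A reader might take the 27% figure as typical. It needs a total SD of only 2 cm.
- A reader might assume that the tape in use is marked more finely than an inch. That is plausible, but the documents do not describe the tape.

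**Conclusion.** The point holds as a minor, avoidable loss of precision. When both waist readings are rounded to the inch, each change score gains random error with an SD of about 1.04 cm. That figure follows from the stated unit alone.

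Its consequence depends on an SD that the documents do not give. Over an assumed total SD of 3 to 8 cm, the loss amounts to between about five completers and one out of 47, and the detectable change moves by less than 1 mm. It would be serious only if waist change varied unusually little between participants. The estimate of mean change is not put in doubt. The conclusion is firm for in-person measurement and open for remote measurement until a unit is stated there.

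**What to change.** In Section 6.1.1, replace the nearest-inch rule with a finer unit at both visits, for example 0.1 cm, or a quarter or eighth of an inch, as the tape's graduations allow. State the same unit in the mailed-tape instructions, so that in-person and remote readings share one resolution. Even a quarter inch removes nearly all of the added error, so the choice can follow what staff and self-measuring participants can read reliably.

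The cost is small: a change to the wording and to the data-entry field, with no added visit or procedure. Section 12.1 requires IRB review and approval before an amendment takes effect. If enrolment has begun, baselines already recorded in whole inches stay coarse. Those pairs would gain only from the finer follow-up reading, and the recording unit used at each visit should be kept in the data.

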6.1.2 Standard of Care Study Procedures

Patient subjects will continue to see their cardiologists for routine clinical care according to their diagnosis.

CONFIDENTIAL

This material is the property of the NYU School of Medicine and Langone Medical Center. Do not disclose or use except as authorized in writing by the study sponsor
Interventional Template Version: 11 January 2019

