6.1.5 Final Study Visit

Final Study Visit (Visit 2; 3 months after baseline visit +/- 2 weeks)

- Record adverse events as reported by participant or observed by investigator.
- Collect follow-up data (surveys, fingerstick lipids, six-minute walk test, waist circumference, body mass index)

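### A participant followed remotely at both time points, with no office visit in between, has the baseline BMI and blood pressure reused as the 3-month values, so the paired change is exactly zero

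*Combined protocol and SAP*

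**What the plan says.** Section 6.1.1 (Measures) sets out a remote route, which opens "In the event all data collection must be remote or the subject prefers remote data collection". On that route:

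- Baseline: "BMI and blood pressure taken on the day of their recent clinical visit will be used for baseline data".
- Month 3: "BMI and blood pressure will be used from the most recent office visit, as close to the 3-month follow-up date as possible".
- Lipids at month 3: "The next available lab data for total cholesterol, HDL and triglycerides will be used". Remote baseline lipids are the latest results in the electronic health record (EHR).

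The same section returns to in-person collection at month 3 where that is possible. The only visit window is in Section 6.1.5: "Final Study Visit (Visit 2; 3 months after baseline visit +/- 2 weeks". It is attached to Visit 2, and the remote paragraphs do not refer to it. Office visits during follow-up are left to routine care under Section 6.1.2: "Patient subjects will continue to see their cardiologists for routine clinical care according to their diagnosis".

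Section 4.2.1 gives the status of these measures: "Primary endpoints include: patients' cardiovascular risk profile (PA, cardiorespiratory fitness, BMI, waist circumference, blood pressure, lipids and Framingham Heart Study Risk Score". Section 9.1 gives the analysis: "Paired t-tests will be used to assess changes in readiness to change number, the 6MWT, BMI, waist circumference, systolic and diastolic BP, lipids". Nothing in Section 9 excludes a reading used twice or sets it to missing.

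**The concern.** The month-3 rule for BMI and blood pressure looks backward to the latest office visit, and the baseline rule points to the visit around enrolment. If no office visit follows, both rules select the same visit. The zero difference then enters the t-test as if it were a measured absence of change.

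This can happen under the protocol as it stands. The remote route is open on preference alone. No office visit near month 3 is arranged for remote participants. Section 5.4 also anticipates virtual visits, so contact with the cardiologist during follow-up need not produce an office reading.

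Sections 9.2 and 9.3 say the pilot is meant to yield preliminary effect sizes and preliminary efficacy data. False zeros shrink both the mean change and its standard deviation, and a later trial planned on these estimates would inherit both errors.

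**Working it through.** **1. The two rules side by side.** Let B be the date of the clinical visit that supplies the remote baseline. The month-3 rule takes the latest office visit available near month 3. If at least one office visit falls after B, a later reading is used, though it may still be far from month 3. If none does, the latest office visit is the one on B, and

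change = reading(B) − reading(B) = 0

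for BMI, systolic pressure and diastolic pressure alike.

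**2. The plan's own figure, used as a base.** Section 9.3 gives 47 evaluable participants, type 1 error 5%, power 80% and effect size 0.41. With the two-sided paired formula:

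n = ((1.960 + 0.842) / 0.41)² = 46.7, rounded up to 47.

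This reproduces the figure. The t-based version needs 49, and power at n = 47 is 78.6%. The attrition step also holds: 59 × 0.8 = 47.2. The plan gives no expected change for BMI or blood pressure, so applying 0.41 to them is an assumption made for illustration.

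**3. Dilution.** Suppose a share r of those analysed has a change of exactly 0, and the rest have mean d and SD 1. Then:

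- mean = (1 − r)d
- SD = √[(1 − r) + r(1 − r)d²]
- effective d = mean / SD

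The documents do not give r, so the range below is assumed. Example for r = 20%: mean = 0.8 × 0.41 = 0.328; SD = √(0.8 + 0.16 × 0.1681) = 0.909; effective d = 0.361.

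| Assumed r | Mean ratio | SD ratio | Effective d | Shortfall in d | Power at n = 47 |
|---|---|---|---|---|---|
| 0 | 1.00 | 1.000 | 0.410 | none | 78.6% |
| 10% | 0.90 | 0.957 | 0.386 | 6% | 73.5% |
| 20% | 0.80 | 0.909 | 0.361 | 12% | 67.8% |
| 30% | 0.70 | 0.857 | 0.335 | 18% | 61.3% |
| 40% | 0.60 | 0.800 | 0.307 | 25% | 54.1% |

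Shortfall is 1 − effective d / 0.41. For effects small relative to their SD, effective d is about d√(1 − r), which gives shortfalls of 5%, 11%, 16% and 23%.

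**4. What changes if such values are set to missing.** The mean among those measured keeps its full size and only n falls, provided that those without a later visit resemble those with one. At d = 0.41, two-sided t:

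| Assumed r | n left | Power, missing | Power, false zeros |
|---|---|---|---|
| 10% | 42 | 73.7% | 73.5% |
| 20% | 38 | 69.2% | 67.8% |
| 30% | 33 | 62.7% | 61.3% |

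The difference in power is negligible. What the change removes is the bias in the estimate.

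**The case against.** The sponsor can fairly say that the rule asks for a reading as near month 3 as can be had, that Visit 2 has a window of two weeks either side, that in-person collection resumes where possible, and that participants keep seeing their cardiologists. All of this shows intent and reduces the number affected. None of it closes the gap. Nearness is an aim, and if the baseline visit is the only one on file it is also the nearest. The window is not tied to EHR readings, and routine care does not guarantee a visit.

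Some objections do stand, and they limit the point:

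- A reader might infer that remote follow-up in general forces a zero change. It does not. Three conditions must coincide: remote at baseline, remote at month 3, and no office visit in between.
- A reader might infer that lipids suffer the same false zero. Their month-3 rule looks forward, so it does not create one. Their problem is that neither end of the interval is limited.
- A reader might infer that 6.1.1 contradicts 6.1.5. The remote route is an explicit exception, so the fault is a missing link, not a conflict.
- A reader might infer that the Framingham score must be distorted. Section 6.1.1 says how the risk model is chosen but does not list blood pressure or lipids among its inputs. Any effect depends on the model used and is an assumption.
- The stated detectable differences in Section 9.3 concern the six-minute walk, steps and achievement of recommended activity, not BMI or blood pressure.

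**Conclusion.** The rule is wrong as written. Followed literally, it produces a change of exactly zero in BMI, systolic and diastolic pressure for anyone remote at both times with no office visit in between. The bias is always toward no change, and the mean change is multiplied by (1 − r). The size cannot be stated from the documents because r is not given: 10% to 40% is an assumed range, and the effective d and power figures further assume that 0.41 applies to these endpoints.

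This should be fixed, but it does not undermine the study. It affects a contingency route of unknown frequency in a one-group pilot with several listed primary endpoints. The unlimited interval for EHR lipids is a secondary matter: a nominal 3-month change may cover a different period.

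**What to change.** In the remote paragraphs of Section 6.1.1:

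1. Accept an EHR value of BMI or blood pressure as the 3-month value only if it is dated after enrolment and lies within the 6.1.5 window, or within one stated wider window.
2. Never use one reading for both time points. Where no reading qualifies, the value is missing.
3. Record the measurement date of every EHR value.
4. As a secondary change, state a look-back limit for baseline EHR lipids and a look-forward limit for the 3-month ones.

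The cost is a few sentences and a date field in REDCap. Fewer remote participants will have a BMI, blood pressure or lipid change. Because visits follow routine care according to diagnosis, that loss may be selective, so the number without a qualifying reading should be reported. No gain in power should be expected; the benefit is that a reported change of zero is one that was measured.
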